#### 4.1.2 Secondary Endpoint(s)

##### 4.1.2a Anxiety Levels

Anxiety levels will be measured using the Hospital Anxiety and Depression Scale (HADS) anxiety subscale (HADS-A) at 3 time points, T1: baseline, T2: post CT-Simulation and T3: post RT day 1. Anxiety levels will be compared between the control and intervention groups at each time point.

##### 4.1.2a Satisfaction

Measured using a survey adapted from Berlin et Al looking at patients' satisfaction with virtual care. This will be measured at time T2. Satisfaction will be compared between control and intervention group.

### 4.2 Specific Design

As this study employs a prospective randomized clinical trial design all consent patients will be randomized 1:1 into either the control group (telephone) or intervention group (videoconferencing) for their pre-treatment RTT-led education session

## **5.0 SELECTION OF PARTICIPANTS**

### **5.1 Inclusion Criteria**

- 18 years or older
- Access to internet connected device with a working microphone and webcam.
- Radical radiotherapy treatment for breast cancer
- Able to communicate in English with/without caregiver.

### **5.2 Exclusion Criteria**

- Previous radiotherapy treatment

### **5.3 Withdrawal of Participation**

Study participants may withdraw their participation at any time.

## **6.0 STUDY INTERVENTION**

Currently the standard of care at Princess Margaret Cancer Center is for all new breast radiotherapy patients is to receive a 30-minute Radiation Therapist (RTT) led telephone pre-treatment education session to explain all procedures and answer patients' questions about their upcoming radiotherapy treatment and associated appointments. Telephone appointments are scheduled for the day before the patients CT-Simulation procedure. Given the preliminary pilot experience for the use of videoconferencing for pre-treatment education the study intervention will employ a 45-minute RTT-led education session with the use of Microsoft Teams also scheduled the day before the patients CT-Simulation appointment. Information given for both sessions will remain consistent across both the control and intervention arm. Videoconferencing will use a standardized slide show with images and graphics to help facilitate patient education and explain procedures, however information shown on the slides will be consistent with that given to patients over the phone in the control arm. The slide show has been previously developed as part of standard care. Patients will be given time to ask questions and a contact to follow up should any questions arise.

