## **Protocol Summary**

**Full Title:** *Virtual vs Phone Education in Radiotherapy – Randomized Clinical Trial*

**Short Title:** *VIPER-RT*

**Study Type:** *Randomized Clinical Trial.*

**Sample Size:** *130 breast cancer patients. All radically treated breast cancer patients at the Radiation Therapy Department in Princess Margaret Cancer Center will be approached*

**Study Population:** *Breast cancer patients being treated with adjuvant breast radiotherapy at the Princess Margaret Cancer Centre (PMCC)*

**Accrual Period:** *7 months*

**Study Design:** *This study will employ a randomized clinical trial in which consented patients will be randomized into one of two groups for pre-treatment radiotherapeutic education. Patients will be placed into either the Control Group – Radiation Therapist led pre-treatment education using telephone calls as part of standard care, or the Intervention Group – Radiation Therapist led pre-treatment education using Microsoft Teams videoconferencing. Patients will be given a set of questionnaires prior to any education (T1), after their CT simulation appointment (T2) and at the end of their first radiation therapy treatment (T3) to assess effectiveness of education at reducing patients' procedural concerns, anxiety and overall satisfaction.*

**Study Duration:** *November 2025 to May 2026*

**Study Intervention:** *Pre-treatment radiotherapy education using video-conferencing software (i.e. Microsoft Teams)*

**Primary Objective:** *To compare whether the use of videoconferencing is more effective than telephone pre-treatment education at reducing breast cancer patients' procedural fears and concerns related to their radiation therapy treatment.*

**Secondary Objective:** *To compare whether the use of video-conferencing is more effective than telephone pre-treatment education at reducing patient reported anxiety levels.*

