### **2.2 Rationale for the study**

At our institution since the COVID 19 pandemic, restrictions to in-person activities are no longer in place. However practices for pre-treatment radiotherapy education with telephone calls have remained, largely as a convenience for staff and patients. Currently, evidence directly comparing these two modalities against each other is lacking.

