#### **2.2.2 Potential Benefits**

The main benefits include reduced radiation therapy related fears and concerns, and anxiety. Since use of videoconferencing allows for a face-to-face educational approach with patients with images and graphics to help facilitate patient understanding, that the use of telephone calls does not have. Patient informational needs and questions are more likely to be answered, resulting in less concerns and fears due to treatment and lower anxiety levels.

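### The objectives ask about videoconferencing versus telephone, but section 6.0 gives the video arm 45 minutes and the telephone arm 30, so a difference can be claimed only for the two packages

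*Protocol*

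**What the plan says.** Section 6.0 defines both arms. As standard care, control patients "receive a 30-minute Radiation Therapist (RTT) led telephone pre-treatment education session". For the other arm, "the study intervention will employ a 45-minute RTT-led education session with the use of Microsoft Teams". Both sessions are therapist-led and take place the day before CT simulation. On content, "Information given for both sessions will remain consistent across both the control and intervention arm". A standardised slide show is described for the video arm only, and its content is said to match what telephone patients are told. The video format is introduced with "Given the preliminary pilot experience for the use of videoconferencing for pre-treatment education"; nothing further explains the longer slot.

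The question is framed elsewhere. Section 2.2 (Rationale) gives the gap as "Currently, evidence directly comparing these two modalities against each other is lacking". The primary objective in the Protocol Summary is "To compare whether the use of videoconferencing is more effective than telephone pre-treatment education", applied to procedural fears and concerns. Sections 3.1.1, 3.1.2a and 3.1.2b and the hypothesis in 3.2 likewise speak of the use of videoconferencing. None of these places mentions session length, which appears only in section 6.0.

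Section 2.2.2 gives the expected mechanism: "Since use of videoconferencing allows for a face-to-face educational approach with patients with images and graphics to help facilitate patient understanding", and then "Patient informational needs and questions are more likely to be answered, resulting in less concerns and fears due to treatment and lower anxiety levels". Extra time is not named there.

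**The concern.** The protocol takes care to equalise content and timing, which suggests that it means to isolate the medium. It then lets scheduled length differ by arm. Length is a plausible rival cause on the protocol's own reasoning: section 2.2.2 expects fewer fears because more questions get answered, and with content held constant, some of a longer session could go to questions.

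What is at stake is the claim. Answered as worded, the objectives would credit videoconferencing with a difference that 15 more scheduled minutes might also produce. A department that read the result as a modality effect might run video in its existing 30-minute slot, a condition on which this trial gives no data. It might also overlook that the tested session takes more scheduled therapist time.

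**Working it through.** **1. What differs between the arms (sections 6.0 and 4.2)**

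| Feature | Telephone | Video |
|---|---|---|
| Delivered by | radiation therapist | radiation therapist |
| Timing | day before CT simulation | day before CT simulation |
| Information | consistent | consistent |
| Slides | not described | standardised slide show |
| Scheduled length | 30 min | 45 min |

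Difference: 45 − 30 = 15 min. Ratio: 45/30 = 1.5. Allocation is 1:1 to these two sessions only. Of the four combinations of {30, 45 min} with {telephone, video}, two occur. Length is constant within each arm by plan, so an effect of length and an effect of medium enter the between-arm difference as a single sum.

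**2. The plan's own sample size (section 7.0)**

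Inputs: difference 0.44, SD 1.35, compound symmetry with correlation 0.08, 3 time points, level 0.05, power 80%. Sidedness is not stated. Two-sided is assumed; one-sided would give 46 per arm, which does not match.

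- n per arm = 2 × (1.960 + 0.842)² × 1.35² × (1 + 2 × 0.08) / (3 × 0.44²) = 57.1, rounded up to 58, or 116 in total.
- With 10% dropout: 58/0.9 = 64.4, rounded up to 65 per arm, or 130 in total.
- SE of the difference in three-point means = √(2 × 1.35² × 1.16 / 3 / 58) = 0.1559. Power = Φ(0.44/0.1559 − 1.960) = 80.6%.

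The stated 116 and 130 reproduce. This point disputes neither.

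**3. An illustration, resting on an assumption**

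The protocol gives no effect of session length. Suppose the medium did nothing and the extra time alone lowered CaTS-PC by d. The baseline questionnaire (T1) precedes any education, so the effect can act only at T2 and T3.

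- Three-point mean: the effect is 2d/3, and P = Φ((2d/3)/0.1559 − 1.960).
- Mean of T2 and T3: SE = √(2 × 1.35² × 1.08 / 2 / 58) = 0.184, and P = Φ(d/0.184 − 1.960).

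| Assumed d | P(significant, favouring video), three-point mean | Same, T2/T3 mean |
|---|---|---|
| 0.11 | 7% | 9% |
| 0.22 | 15% | 22% |
| 0.33 | 29% | 43% |
| 0.44 | 47% | 67% |

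With no effect of time or medium, the figure is 2.5% in either column. As statements about the two packages, these significant results would be correct. They would be wrong only if read as an effect of the medium.

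**The case against.** The best reply is that nothing here is hidden or contradictory. Both lengths are stated together in section 6.0, which promises equal information and never equal time. The control is existing practice, so this is a pragmatic comparison, and the objectives use short labels for arms defined elsewhere, as protocols often do. The telephone session also exists to answer questions, and section 6.0 offers time for questions without limiting it to one arm. The longer slot may simply be what a slide show needs, and so be part of the video format. The lengths are also scheduled; delivered minutes may differ.

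Most of this stands. The lengths are disclosed, the comparator is legitimate, and length may belong to the format. But the protocol never says that it does, and if it does, that is a reason to name the 45-minute session in the objectives. Disclosure in section 6.0 does not repair a rationale and objectives that pose a modality question without mentioning length.

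A reader might go further and infer that the randomised comparison is biased, or that the sessions must be made equal. The documents do not support either: randomisation protects the contrast between the two packages, and comparing a new package with usual care is a valid aim.

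**Conclusion.** The point holds as one about interpretation. The trial can support a statement about a 45-minute slide-supported Teams session against the standard 30-minute call. It cannot support attributing a difference in CaTS-PC, HADS-A or satisfaction to videoconferencing alone, and no statistical analysis plan could change that, because the aliasing is set by the design.

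The size that can be stated from the document is 15 extra scheduled minutes, 1.5 times control. The probabilities in the illustration rest on assumed length effects, a zero effect of the medium and the section 7.0 inputs taken at face value; they are not estimates. A reader might also take the 80.6% power as the chance that a time-only effect of 0.44 would be declared significant. That does not follow, because it would place the effect at T1 as well, before any education has taken place. Nor does the document show that extra time has any effect at all.

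The change should be made because it corrects what the trial can conclude at little cost.

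**What to change.** In the primary and secondary objectives (Protocol Summary and sections 3.1.1, 3.1.2a and 3.1.2b) and the hypothesis (section 3.2), state the comparison as: 45-minute slide-supported Microsoft Teams session versus standard 30-minute telephone session, as defined in section 6.0. This also supplies the telephone comparator that 3.1.1, 3.1.2a and 3.2 leave out. Add that conclusions will be limited to this comparison.

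Optionally, log delivered minutes for each session and report them by arm descriptively. They should not enter the primary analysis as a covariate, because they arise after randomisation, and they would not separate length from medium in any case.

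Session lengths, randomisation, sample size and endpoints stay as planned. The cost is a narrower claim, an REB amendment under section 9.2 and, if minutes are logged, one extra field per session (up to 130 entries).

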## **7.0 STATISTICS**

A total sample of 116 patients (58 Telephone, 58 Videoconference), measured at 3 time points, will achieve 80% power at a 0.05 significance level to detect a 0.44 mean difference in Cancer Treatment Survey (CaTS) Procedural Concerns subscale scores between groups using a repeated measures design. The assumed standard deviation is 1.35, with a compound symmetry covariance structure and autocorrelation of 0.08. Based on the study by Halkett et al. (2018) for the same subscale score, the mean difference was derived from the estimate at the Prior to Treatment Planning (F1) time point, the assumed standard deviation is 25% lower than the estimated value of 1.80 from all confidence intervals, and the autocorrelation value was estimated from the reported Cohen's d at the Treatment completion (F3) time point. Anticipating a 10% dropout rate, the target recruitment sample is 130 (65 Telephone, 65 Videoconference). Sample size was calculated using PASS 2025, version 25.0.2.

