### 4.1 Endpoints

#### 4.1.1 Primary Endpoints

This will be measured using the Cancer Treatment Survey (CaTS) procedural fears and concerns subscale (CaTS-PC) at 3 time points, T1 baseline, T2 post CT Simulation and T3: post RT day 1. These measurements will be compared between the control and intervention group at each time point.

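### The 80% power counts the pre-education baseline (T1) as a third outcome carrying the full 0.44 effect; with T2 and T3 only, 116 patients give about 67%

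*Protocol*

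**What the plan says.** Section 7.0 bases the sample size on three measurements per patient: "A total sample of 116 patients (58 Telephone, 58 Videoconference), measured at 3 time points, will achieve 80% power at a 0.05 significance level". The target is "to detect a 0.44 mean difference in Cancer Treatment Survey (CaTS) Procedural Concerns subscale scores between groups using a repeated measures design". The variance inputs follow: "The assumed standard deviation is 1.35, with a compound symmetry covariance structure and autocorrelation of 0.08". Allowing for 10% dropout, the recruitment target is 130, or 65 per arm.

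Section 4.1.1 identifies the three measurements of the primary endpoint: "at 3 time points, T1 baseline, T2 post CT Simulation and T3: post RT day 1". It adds that the arms are to be compared at each of them. The Study Design paragraph of the Protocol Summary fixes when T1 is taken: "Patients will be given a set of questionnaires prior to any education (T1), after their CT simulation appointment (T2"). Section 6.0 schedules the session in both arms for the day before CT simulation, and section 4.2 sets 1:1 randomisation.

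**The concern.** A baseline taken before the arms are treated differently cannot show a treatment effect. In a randomised trial its expected between-arm difference is zero. T1 can reduce residual variance as a covariate, but it is not a third observation of the outcome. If the calculation treats it as one, it credits the trial with information it will not collect.

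The primary comparison is what is at stake. The protocol accepts a 20% chance of missing a true 0.44 difference. If only T2 and T3 carry the effect, that chance is about one third, and a null result would be read as coming from an adequately powered trial. If the analysis followed the power calculation literally and averaged all three visits, the expected contrast would also shrink to two thirds of 0.44.

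**Working it through.** **Inputs from section 7.0:** difference d = 0.44, SD σ = 1.35, compound symmetry with ρ = 0.08, α = 0.05, n = 58 per arm. The protocol does not say whether the test is one- or two-sided. Two-sided is assumed here, and it reproduces the stated size.

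**Formulas (normal approximation):**
- Variance of a patient's mean over m visits: V = σ²[1 + (m − 1)ρ]/m
- Size per arm for 80% power: n = 2(1.96 + 0.8416)²V/d²
- Power: Φ(d/√(2V/n) − 1.96)

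**Step 1: reproduce the protocol's figure.** With m = 3 and 0.44 at every visit:
- V = 1.8225 × 1.16/3 = 0.7047
- n = 2 × 7.849 × 0.7047/0.1936 = 57.1, so 58 per arm and 116 in total
- Power at 58 per arm is 80.6% (79.9% with the noncentral t)
- Dropout: 58/0.9 = 64.4, so 65 per arm and 130 in total

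The stated figures are matched. The same formula with m = 2 needs 80 per arm and with m = 1 needs 148, so neither explains 58. One-sided testing with m = 3 would give 88% power at 58 per arm, which does not match either.

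**Step 2: T2 and T3 only, 0.44 at both.**
- V = 1.8225 × 1.08/2 = 0.9842
- n = 2 × 7.849 × 0.9842/0.1936 = 79.8, so 80 per arm
- Power at 58 per arm: 0.44/√(2 × 0.9842/58) = 2.389, and Φ(2.389 − 1.96) = 66.6% (65.9% with the noncentral t)

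**Step 3: T2 and T3 with T1 as covariate.**
- V = σ²[(1 + ρ)/2 − ρ²] = 1.8225 × (0.54 − 0.0064) = 0.9725
- n = 78.9, so 79 per arm
- Power at 58 per arm is 67.1% (66.4% with the noncentral t)
- Detectable difference at 80% power: 2.8016 × √(2 × 0.9725/58) = 0.51

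At ρ = 0.08 the baseline adds only half a percentage point.

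**Step 4: other readings, 58 per arm.**

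| Analysis | Power |
|---|---|
| Mean of all three visits, zero difference at T1 (contrast 0.44 × 2/3 = 0.293) | 46.9% |
| One post-education visit alone | 41.9% |
| One post-education visit, T1 as covariate | 42.1% |
| Mean of T2 and T3 minus T1 | 32.1% |
| Mean of T2 and T3, one-sided 0.05 | 77.1% |
| Mean of T2 and T3, no dropout (65 per arm) | 71.5% |

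**Step 5: sensitivity to the correlation.** With T1 as covariate, power for the mean of T2 and T3 at SD 1.35 is 65.0% at ρ = 0.2, 65.0% at 0.3, 66.6% at 0.4, 69.9% at 0.5, 75.4% at 0.6 and 83.3% at 0.7. The protocol's own three-visit calculation falls over the same range, to 50.1% at ρ = 0.7.

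**The case against.** Section 7.0 speaks only of a repeated measures design. It does not say that the contrast is a time average or that T1 carries 0.44, so the mechanism is inferred. That is fair, but the inference is strong: the three-visit average returns exactly 58, and the alternatives tried do not.

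A second objection is that 67% is not the power of any analysis the protocol defines. It assumes that T2 and T3 are pooled with a constant 0.44 at both, whereas section 4.1.1 compares the arms at each time point. This stands as a qualification, and it makes the position worse: a single post-education visit has about 42% power. So 67% is the favourable reading. Likewise, 46.9% applies only if T1 really is averaged in, which the protocol does not state.

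Third, the exact figure can be disputed. The noncentral t puts it nearer 66%, and it depends on an SD set 25% below the estimated 1.80 and on a very low correlation. The one-point gap does not matter. The SD and the correlation are separate questions, and correcting the SD upwards would lower the power further. A correlation high enough to bring baseline-adjusted power to 80% lies between 0.6 and 0.7, far from 0.08, and would also invalidate the protocol's own calculation.

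Finally, the analysis model may sit in a SAP that is not at hand. The power claim, its inputs and the timing of T1 are all in the protocol, so the stated figure is wrong whatever the SAP says.

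**Conclusion.** The concern holds. The stated 80% depends on a treatment difference at a visit that precedes the treatment. On the protocol's own inputs, 116 evaluable patients have about 67% power for a 0.44 difference averaged over T2 and T3, or 80% power for about 0.51. The risk of missing a true 0.44 difference is therefore about 33%, not 20%.

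This assumes a two-sided 0.05 test, a constant 0.44 effect at T2 and T3, SD 1.35 and ρ = 0.08. None of the alternatives at ρ = 0.08 that give T1 zero effect reaches 80%, including one-sided testing and complete follow-up of all 130 patients.

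**What to change.** Amend section 7.0 to:
- name T2 and T3 as the outcome measurements (m = 2) and T1 as the baseline covariate;
- say that the test is two-sided and that the contrast is the mean of T2 and T3, and align section 4.1.1 with this;
- replace the power statement: 116 evaluable patients give about 67% power for 0.44, or 80% power for about 0.51, at SD 1.35 and ρ = 0.08, preferably with the range over plausible correlations;
- withdraw the claim of 80% power for 0.44.

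This costs one paragraph and a less favourable stated power. Recruitment, visits and questionnaires do not change. If the sponsor prefers to keep 80% power for 0.44, the baseline-adjusted design needs 79 per arm, that is 158 evaluable and 158/0.9 = 175.6, so about 176 recruited. That choice is the sponsor's and is not needed to correct the statement.

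### The within-patient correlation of 0.08 behind the sample size has no adequate stated source, and the 80% power is lost once the correlation exceeds about 0.08 to 0.09

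*Protocol*

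**What the plan says.** Section 7.0 of the protocol gives all the inputs to the sample size.

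- Size: "A total sample of 116 patients (58 Telephone, 58 Videoconference), measured at 3 time points".
- Power and significance level: "will achieve 80% power at a 0.05 significance level". Sidedness is not given.
- Effect: "to detect a 0.44 mean difference in Cancer Treatment Survey (CaTS) Procedural Concerns subscale scores between groups using a repeated measures design".
- Standard deviation: "The assumed standard deviation is 1.35".
- Covariance: "with a compound symmetry covariance structure and autocorrelation of 0.08".
- Origin of the correlation: "the autocorrelation value was estimated from the reported Cohen's d at the Treatment completion (F3) time point".

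No formula, intermediate figure or sensitivity range accompanies the value of 0.08. Section 4.1.1 names the three time points as T1 baseline, T2 after CT simulation and T3 after the first radiotherapy treatment. The Protocol Summary places T1 before any education.

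**The concern.** A Cohen's d at one time point is a mean difference divided by a standard deviation. It describes how far apart the groups are, not how closely one patient's score at one visit tracks the same patient's score at another. A correlation can be extracted only with something more, such as the standard deviation of change or a model standard error. Section 7.0 names neither.

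The value matters because of how it enters. When the arms are compared on the average of three scores, a correlation near zero makes each repeat count almost as a new patient. At 0.08, a patient's baseline score accounts for 0.08² = 0.0064, or 0.6%, of the variance of the same scale in the same patient later on. If the true correlation is higher, the design as powered falls short of its stated 80%.

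The average also includes T1. Randomisation makes the expected difference between arms at T1 zero, so a calculation that expects 0.44 there counts an effect that cannot yet exist.

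**Working it through.** **Inputs, all from section 7.0:** n = 58 per arm; difference δ = 0.44; SD = 1.35; m = 3 time points; compound symmetry with correlation r = 0.08; significance level 0.05. A two-sided test is assumed because it reproduces the stated size. A one-sided test gives 46 per arm, and a first-order autoregressive structure gives 110 in total; neither matches.

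**Step 1: reproduce the plan.** Under compound symmetry the variance of a patient's three-time mean is SD²(1 + 2r)/3.

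- At r = 0.08: 1.8225 × 1.16 / 3 = 0.7047, so the effective SD is 0.8395.
- n per arm = 2 × (1.96 + 0.8416)² × 0.7047 / 0.44² = 57.1, rounded up to 58, or 116 in total.
- Power at 58 per arm is 79.9% by noncentral t with 114 degrees of freedom (80.6% by the normal approximation).
- Dropout: 58 / 0.9 rounds up to 65 per arm, or 130.

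The stated figures reproduce, which identifies the calculation and the role of r in it.

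**Step 2: vary only r.** Power is by noncentral t at 58 per arm; n per arm for 80% is by the normal approximation.

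| r | Variance of mean | Power, 116 patients | n per arm for 80% |
|---|---|---|---|
| 0.08 | 0.7047 | 79.9% | 58 |
| 0.2 | 0.8505 | 72.2% | 69 |
| 0.3 | 0.9720 | 66.4% | 79 |
| 0.5 | 1.2150 | 56.8% | 99 |
| 0.7 | 1.4580 | 49.4% | 119 |

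Below 0.08 the power is higher (85% at r = 0). The 80% is lost above about 0.08 by noncentral t, or 0.09 by the normal approximation. The values above 0.08 are assumed.

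**Step 3: place the effect only after education.** With a difference of 0 at T1 and 0.44 at T2 and T3, the expected difference in the three-time mean is (0 + 0.44 + 0.44)/3 = 0.293. With the same variances and 58 per arm, power is about 46% at r = 0.08, 36% at 0.3, 30% at 0.5 and 25% at 0.7.

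**Step 4: compare the mean of T2 and T3 with T1 as a covariate.** The residual variance is SD²[(1 + r)/2 − r²], and the effect is 0.44.

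- At r = 0.08: 1.8225 × (0.54 − 0.0064) = 0.9725; power 66%.
- At r = 0.3: 1.8225 × (0.65 − 0.09) = 1.0206; power 64%.
- At r = 0.5: 1.8225 × (0.75 − 0.25) = 0.9113; power 69%.
- At r = 0.6: 1.8225 × (0.80 − 0.36) = 0.8019; power 75%.
- At r = 0.7: 1.8225 × (0.85 − 0.49) = 0.6561; power 83%.

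Power reaches 80% only near r = 0.67.

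**The case against.** The best defence is that nothing in section 7.0 is miscalculated: the inputs give 58 per arm and 80% power, and the recruitment target follows. That stands. The dispute is about an input, not the arithmetic.

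It can also be said that the section does not claim that d alone was used. If the cited trial standardised its d by a change-score or model-based SD, then d together with the section's SD of 1.80 and a mean difference might yield a correlation. This too stands in part. A reader might infer that the derivation is invalid, but that cannot be shown without the cited trial. What can be shown is that the section names a source which is insufficient by itself and gives no derivation.

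A reader might also infer that 0.08 is known to be wrong. The protocol contains no observed CaTS-PC correlation, so calling the value implausibly low is a judgement, and the size of the shortfall depends on the range assumed.

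A third tempting reading is that baseline adjustment recovers the lost power, by 69 − 57 = 12 points at 0.5 and 83 − 49 = 34 points (33 before rounding) at 0.7. Those subtractions compare unlike quantities: the three-time figures assume a 0.44 difference at T1, and the adjusted ones do not. Nor is recovery general, since adjusted power stays below 80% until about 0.67.

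Finally, the choice of covariates is commonly left to an analysis plan. Its absence from the protocol is not criticised here. The point concerns a number that section 7.0 itself fixes and the power claimed from it.

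**Conclusion.** The point holds as a weakness in a stated assumption. The 0.08 lacks an adequate stated basis, and the 80% has no margin against it: on the protocol's own formula, power falls to 72% at a correlation of 0.2 and to 57% at 0.5. Separately, even at 0.08 the 80% requires a 0.44 difference at T1. For an effect confined to T2 and T3, the same average has about 46% power.

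These figures rest on a two-sided test, a difference of 0.44, an SD of 1.35, compound symmetry and 58 analysed patients per arm. The 25% reduction of the SD from 1.80 is a separate matter and is left as stated. The trial can still be run; what needs correction is the claim about its power.

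**What to change.** In section 7.0:

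1. Replace 0.08 with a correlation estimated from repeated CaTS-PC scores, showing the derivation, or with a declared range such as 0.3 to 0.7.
2. Restate the power of 116 patients over that range for the comparison of T2 and T3 with T1 CaTS-PC as a covariate, so that no effect is credited to the measurement before education. With the other inputs unchanged, the figures are those in step 4 of the working.

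Leave the number of patients as it is, and do not describe the adjustment as restoring 80% in general. The cost is a re-run of the calculation, about two sentences of text and a less favourable stated power. No new data are needed, because T1 is already collected.
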